#### 5.2. Statistical Analysis

All data will be collected by the site and entered into a database. Subjects will be assigned an ID number. Data analysis will be performed without patient identification. Statistical analysis will be performed using standard descriptive statistics. Analysis will include stratification based on the amount of preoperative angle kappa as follows: 0 to < 0.3 mm, 0.3 mm to < 0.4 mm and 0.4 mm or higher. Data analysis will be conducted by a third-party consultant.

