#### 3.4. Measurements and evaluations

1. Visit 1: Informed consent process will be conducted at this visit. Assessments include best-corrected Snellen visual acuity, manifest refraction, intraocular pressure (IOP) using Goldman tonometer, slit lamp examination including dilated fundus exam,

- 2. Visit 2: The surgeon may use his preferred cataract extraction technique (manual or laser). The lens will be implanted in the bag. The following information will be captured the day of surgery: phaco technique (manual or laser), lens implanted and power, target refraction for IOL power implanted using Barrett Universal II, Hill RBF, Holladay 2, Holladay 1 and SRK-T formulas, residual astigmatism and axis for Barrett Toric Calculator and Barrett TK for toric power calculation (if applicable), additional surgical procedures, intraoperative complications, and any device deficiencies. The surgeon's standard post cataract surgery treatment will be used in all patients.
- 3. Visit 3: Slit lamp examination, manifest refraction, UCVA, BCVA, UCIVA (at 60 cm), DCIVA (at 60 cm), UCNVA (at 40 cm) and DCNVA (at 40), and UCNVA at best distance, IOP, IOL orientation, dilated fundus exam (as deem necessary by the investigator), angle kappa measured using OPD III scan, visual symptoms, patient satisfaction and spectacle independence questionnaires, adverse events and any device deficiencies.

All adverse events and complaints will be monitored and recorded at all study visits.

**Table 1.** Visits and Study Assessments

	Visit 1 Screening	Visit 2 and 2A DOS	Visit 3 3-Month 90 ±15 days
Informed Consent	X		
Inclusion/Exclusion	X	X	
Demographics/PMH/Ocular history	X		
Snellen BCVA	X		
Snellen Manifest refraction	X		
UCVA ETDRS (4m)			Χ*
Manifest refraction – Max Plus			X
BCVA ETDRS (4m)			Χ*
UCIVA ETDRS (60 cm)			Χ*
DCIVA ETDRS (60 cm)			Χ*

UCNVA ETDRS (40 cm)			X*
DCNVA ETDRS (40 cm)			Χ*
UCNVA at best distance			Χ*
Intraocular Pressure (Goldman)	X		X
SLE	X		X
Dilated fundus exam	X		χ†
Cataract density / type	X		
OPD III scan	X		X
IOL Power calculation using different formulas	X		
Toric IOL calculation	X**		
Intraoperative data		X	
Toric IOL position		X**	χ†
Questionnaires	X		X
AE/Device deficiencies		X	X

8

X To be performed as scheduled

- \* Monocular and binocular testing
- \*\* If a toric lens is used
- † To be performed as deem necessary by the investigator

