#### 5. STATISTICAL CONSIDERATIONS

#### 5.1. Sample size

A total of 30 subjects will be enrolled. In order to calculate the sample size, we need to know an accurate estimate of the standard deviation of the outcome measure which we do not know; therefore, we consider this study a pilot trial. When estimating the sample size for a pilot study, the simplest method is to apply a sample size rule of thumb. Browne suggests a general flat rule to 'use at least 30 subjects or greater to estimate a parameter'.

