#### 5.3. Study Endpoints:

#### 1. Primary Endpoint:

a. Effect of angle kappa in visual disturbances and patient satisfaction

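### The primary angle-kappa question rests on unadjusted summaries in three small non-randomised bands; an estimate with an interval, adjusted for the Visit 1 score where the scale matches, should stand beside them

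*Combined protocol and SAP*

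**What the plan says.** Section 5.3 of the combined protocol and SAP sets the primary endpoint as "Effect of angle kappa in visual disturbances and patient satisfaction". Section 5.2 gives the whole method: "Statistical analysis will be performed using standard descriptive statistics". It adds: "Analysis will include stratification based on the amount of preoperative angle kappa as follows: 0 to < 0.3 mm, 0.3 mm to < 0.4 mm", with a third band from 0.4 mm upward. Sections 5.1 to 5.4 name no model, contrast, confidence interval, covariate or change from Visit 1.

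Section 5.1 fixes the size: "A total of 30 subjects will be enrolled". It calls the study a pilot because "we need to know an accurate estimate of the standard deviation of the outcome measure which we do not know". Section 8.3 marks the method of assigning subjects as not applicable, so the bands are formed by anatomy alone.

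Table 1 marks questionnaires at Visit 1 and Visit 3. For Visit 3, section 3.4 lists "visual symptoms, patient satisfaction and spectacle independence questionnaires". The content of the Visit 1 questionnaire is not stated. Table 1 also schedules "Manifest refraction – Max Plus" at Visit 3; refractive accuracy and residual astigmatism are secondary endpoints in section 5.3.

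**The concern.** The plan speaks of an effect of kappa but describes only raw scores in bands that nobody assigned. Patients in the high band may differ from those in the low band in other ways that bear on halos, glare or satisfaction. Some differences will be chance, since the bands are small. Others may be systematic, for example in age or in toric versus non-toric lens, and a larger sample would not remove those. A raw band summary cannot separate either kind from kappa, and with no interval planned the reader cannot see how uncertain the difference is.

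A baseline questionnaire is already scheduled. If it uses the same scale as Visit 3, leaving it out may waste precision and leaves uncorrected any band difference in how much patients complained before surgery.

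**Working it through.** **Inputs from the documents.** N = 30 (section 5.1); three kappa bands (section 5.2); questionnaires at both visits (Table 1); outcome standard deviation unknown (section 5.1), so results are in SD units.

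**Assumptions.** Visit 1 to Visit 3 correlation 0 to 0.6; band splits 10/10/10, 15/9/6 and 20/6/4; a roughly continuous score; two-sided 95% intervals. The documents give none of these.

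**1. The plan's own figure.** N = 30 agrees with the rule it cites, "use at least 30 subjects or greater to estimate a parameter". There is no formula to reproduce.

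**2. What the bands can show.** The mean band size is 30/3 = 10. For lowest versus highest band at 10/10/10, SE = √(1/10 + 1/10) = 0.447 SD. With t on 27 df (2.052), the 95% half-width is 2.052 × 0.447 = 0.92 SD. The same calculation gives 0.99 SD at 15/9/6 and 1.12 SD at 20/6/4.

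**3. Chance imbalance.** Take a covariate unrelated to kappa. The probability that its mean differs by more than 0.5 SD between the outer bands is 2 × [1 − Φ(0.5/SE)]:
- 10/10/10: 0.5/0.447 = 1.118, giving 26%
- 15/9/6: SE 0.483, giving 30%
- 20/6/4: SE 0.548, giving 36%

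If the covariate correlates r with the outcome, a 0.5 SD imbalance shifts the raw difference by 0.5 × r: 0.15 SD at r = 0.3 and 0.25 SD at r = 0.5.

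**4. Precision from adjusting for one baseline score.** For the slope on continuous kappa, the ratio of adjusted to unadjusted interval width is √[(1 − ρ²) × 28/27] × t(27)/t(28). Here √(28/27) = 1.018 and t(27)/t(28) = 2.052/2.048 = 1.002, so the penalty factor is 1.020.

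| ρ (assumed) | √(1 − ρ²) | × 1.020 | Interval |
|---|---|---|---|
| 0 | 1.000 | 1.020 | 2% wider |
| 0.2 | 0.980 | 0.999 | unchanged |
| 0.3 | 0.954 | 0.973 | 3% narrower |
| 0.5 | 0.866 | 0.883 | 12% narrower |
| 0.6 | 0.800 | 0.816 | 18% narrower |

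Break-even is at ρ = √(1 − 1/1.020²) = 0.197, about 0.2. At ρ = 0.5 the gain is worth 1/0.883² = 1.28, or 28% more patients.

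**5. Cross-check on the planned bands.** With one covariate the SE ratio is √[(1 − r²) × 26/25]: 1.02, 0.97 and 0.88 at r = 0, 0.3 and 0.5. Simulating 20,000 studies of 10/10/10 at each correlation gave 1.023, 0.975 and 0.889. The slope and band calculations agree.

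**6. On the correlation scale.** By chance alone, the correlation of kappa with any unrelated covariate lies within about ±1.96/√29 = ±0.364 in 95% of studies. Through a covariate correlated 0.5 with symptoms, this can contribute 0.364 × 0.5 = 0.18 to the kappa-symptom correlation. That is the 95% limit of one term and not a maximum.

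**7. Cost of a three-covariate sensitivity model.** If the covariates explain nothing, the width ratio is √(28/25) × t(25)/t(28) = 1.058 × (2.060/2.048) = 1.064, about 6% wider.

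**The case against.** **It is a pilot.** The plan is descriptive and states no test, alpha or power, so nothing it claims is invalidated. That stands and limits the severity. It does not stop raw band differences from being read as the effect that section 5.3 names, and section 11 plans publication.

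**The gain is not assured.** A reader might infer that precision is certainly lost. The documents do not support that: they give no correlation and do not say what the Visit 1 questionnaire measures. Satisfaction with the implanted lens cannot be scored before surgery. The Introduction links postoperative symptoms to the multifocal optic, so preoperative answers may predict them weakly. Below a correlation of about 0.2, adjustment gains nothing.

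**Adjustment removes little of the chance noise.** At N = 30 the kappa-symptom correlation itself varies by about ±0.36 with no true effect. A covariate with r = 0.5 accounts for r² = 25% of that variance, leaving 75%. This stands, and it is why the interval matters at least as much as the covariate.

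**Refraction.** A reader might infer that residual refraction should be adjusted for routinely, on the ground that surgery aimed at plano (section 3.2) leaves mainly prediction error. Nothing in the documents establishes that. Refraction is measured at the same visit as the outcome, it underlies the secondary endpoints, and section 1 lists outcomes among the things kappa may affect. Conditioning on it may remove part of the kappa effect.

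**Eyes and patients.** Kappa and refraction are per eye and questionnaires per patient, so a model needs a stated rule for joining them. This stands and is met in the fix.

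**Conclusion.** The point holds in conditional form. The primary question is left to unadjusted description in three non-randomised bands averaging 10 patients. A scheduled baseline questionnaire has no stated use, and no measure of uncertainty is planned. Precision may be lost, and chance or systematic differences between patients may pass for a kappa effect.

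The change in interval width runs from about 2% wider to 18% narrower for assumed correlations from 0 to 0.6. With the assumed splits, an unrelated covariate is out of balance by more than 0.5 SD between the outer bands in 26% to 36% of studies. All these figures rest on assumed correlations, assumed band sizes and a roughly continuous score.

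A reader might also infer that adjustment would isolate the effect of kappa. It would not: with an unassigned exposure, other confounding can remain. The change is worth making because it is cheap; the study does not fail without it.

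**What to change.** In section 5.2, keep the descriptive bands and add:

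- **Main estimate.** A patient-level regression of the Visit 3 score on continuous preoperative kappa, using one stated per-patient summary such as the mean of the two eyes. Report the slope with a 95% confidence interval.
- **Adjustment.** Report the slope unadjusted and adjusted for the Visit 1 score wherever the same scale is given at both visits, most plausibly visual symptoms. For satisfaction with the implanted lens, report the unadjusted slope only. State which scales are used at Visit 1.
- **Optional sensitivity model.** Add absolute residual spherical equivalent and cylinder from Visit 3, summarised per patient in the same way. Label it a sensitivity analysis and note that it estimates the kappa effect not running through refraction.
- **Wording.** Call the result an association and say that other confounding may remain.

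The cost is SAP text and a few models on data already scheduled, with no new visits. Adjustment uses one degree of freedom (three in the sensitivity model), and intervals are slightly wider if the Visit 1 to Visit 3 correlation is below about 0.2. The wording should be fixed before the Visit 3 data are examined, so that covariates are not chosen after the event.

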#### 5.3. Study Endpoints:

#### 1. Primary Endpoint:

a. Effect of angle kappa in visual disturbances and patient satisfaction

#### 2. Secondary Endpoints:

- a. Proportion of eyes within ±0.50 D of intended target (plano) when using the Barrett Universal II formula for IOL power calculation
- b. Proportion of eyes within  $\pm 0.50$  D of intended target (plano) when using the Hill RBF formula for IOL power calculation
- c. Proportion of eyes within ±0.50 D of intended target (plano) when using the Holladay 2 formula for IOL power calculation
- d. Proportion of eyes within ±0.50 D of intended target (plano) when using the Holladay 1 formula for IOL power calculation
- e. Proportion of eyes within ±0.50 D of intended target (plano) when using the SRK-T formula for IOL power calculation
- f. Proportion of eyes with residual astigmatism of 0.50 D or less when using the Barrett Toric Calculator
- g. Proportion of eyes with residual astigmatism of 0.50 D or less when using the Barrett TK for toric power calculation

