#### 1. OBJECTIVE:

The purpose of this study is to evaluate the effect of angle kappa in outcomes, patient satisfaction and visual disturbances in patients with and without astigmatism implanted bilaterally with the PanOptix toric and non-toric IOL after routine cataract surgery as well as to evaluate intraocular (IOL) calculation formulas.

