#### **3.3. Study Visit Schedule and Assessments** (Table 1).

- 1. **Visit Schedule:** Subjects will be examined at the following intervals:
  - 1. Visit 1: Screening and enrollment: Preoperative evaluation completed not more than eight weeks before surgery
  - 2. Visit 2: Day of Surgery for each eye
  - 3. Visit 3: Month 3: 90 ±15 days postoperative after second eye surgery

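### Secondary endpoints a–e score all five IOL formulas against plano on the same postoperative refraction, so as written they are one proportion reported five times

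*Combined protocol and SAP*

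**What the plan says.** Evaluating the formulas is part of the study's purpose. Section 1 adds it to the angle kappa aim: "as well as to evaluate intraocular (IOL) calculation formulas".

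Section 5.3 gives five of its seven secondary endpoints to this. Endpoint a reads "Proportion of eyes within ±0.50 D of intended target (plano) when using the Barrett Universal II formula for IOL power calculation". Endpoints b to e are worded the same way for Hill RBF, Holladay 2, Holladay 1 and SRK-T. All five name plano as the reference.

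The data come from two visits described in section 3.4. On the day of surgery the site records "target refraction for IOL power implanted using Barrett Universal II, Hill RBF, Holladay 2, Holladay 1 and SRK-T formulas", which is one predicted value per formula for the lens actually placed. After surgery the refraction is measured once: "Visit 3: Slit lamp examination, manifest refraction, UCVA, BCVA". Section 3.3 lists a single postoperative visit: "Visit 3: Month 3: 90 ±15 days postoperative after second eye surgery". Section 3.2 sets the surgical target for both eyes at plano, within 0.25 D, without reference to any formula.

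On analysis, section 5.2 says "Statistical analysis will be performed using standard descriptive statistics". It does not define prediction error or a comparison between formulas. On size, section 5.1 says "A total of 30 subjects will be enrolled".

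**The concern.** A formula's accuracy is judged by how far the achieved refraction falls from what that formula predicted for the implanted lens. Endpoints a–e instead hold the reference fixed at plano. With one lens and one refraction per eye, nothing in the definition changes from one formula to the next.

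Two things can then go wrong. If the third-party analyst follows the text, the report shows five equal proportions, which a reader could take as evidence that the formulas are equally accurate. If the analyst uses the Visit 2 predictions instead, the result is informative but is no longer the endpoint that was written, and the choice may be made after the data are seen.

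**Working it through.** **Inputs from the documents.** Reference plano and tolerance ±0.50 D for all five endpoints (section 5.3). One postoperative manifest refraction per eye (sections 3.3 and 3.4, Table 1). One prediction per formula for the implanted power (section 3.4, Visit 2). 30 subjects, hence up to 30 × 2 = 60 eyes (section 5.1). The plan states no expected proportion, SD or bias for any formula, so it has no figure to reproduce for a–e.

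**Step 1: the endpoint as written.** Let R_i be the Visit 3 refraction of eye i and P_ik the prediction of formula k for the lens implanted in that eye.

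- As written, formula k scores the share of eyes with |R_i − 0| ≤ 0.50 D. This expression contains no k.
- Against its own prediction, formula k scores the share of eyes with |R_i − P_ik| ≤ 0.50 D. This one does depend on k.

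The equality of the five written proportions is therefore exact and needs no assumption about accuracy.

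**Step 2: one eye.** Suppose R = −0.40 D, formula A predicted −0.10 D and formula B predicted +0.20 D.

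- As written: |−0.40| ≤ 0.50, a hit for both.
- Against own prediction: A, −0.40 − (−0.10) = −0.30 D, a hit; B, −0.40 − 0.20 = −0.60 D, a miss.

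**Step 3: how large a difference could be hidden.** Assume the prediction error of a formula is normal with mean b and SD s. Then

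P(s, b) = Φ((0.5 − b)/s) − Φ((−0.5 − b)/s).

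All values of s and b below are assumptions.

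| s (D) | b (D) | Within ±0.50 D of own prediction | Below s = 0.35, b = 0 | Eyes of 60 |
|---|---|---|---|---|
| 0.35 | 0 | 84.69% | 0 | 0 |
| 0.40 | 0 | 78.87% | 5.82 points | 3.5 |
| 0.45 | 0 | 73.35% | 11.34 points | 6.8 |
| 0.50 | 0 | 68.27% | 16.42 points | 9.9 |

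With equal SDs of 0.40 D and a mean error in one formula only, the gap is 78.87 − 77.45 = 1.42 points for b = 0.10 D and 78.87 − 73.33 = 5.54 points for b = 0.20 D. With equal SDs and no bias it is 0. The written endpoint shows 0 in every row.

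**Step 4: simulation check.** In 5,000 simulated trials of 60 eyes, formula biases of 0, 0.02, −0.05, 0.15 and 0.25 D, between-formula noise with SD 0.15 D and a common error SD of 0.40 D were assumed. The written endpoint averaged 76.0% for all five formulas, and the five values were identical in every trial. Scored against own predictions, the averages were 75.7%, 75.7%, 75.5%, 72.9% and 68.2%.

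**The case against.** The strongest reply is that the phrase about using a given formula can be read counterfactually: how far from plano would the eye have been had that formula chosen the lens? That distance is approximately R_i − P_ik, so plano is the common aim and each formula gets its own result. The plan's vocabulary supports this. Section 3.4 uses target refraction in a formula-specific sense for the same five formulas in the same order, and those five recorded values would serve no stated endpoint otherwise. This is a good argument about intent, and prediction error probably was meant. It does not rescue the text, because neither section 5.2 nor section 5.3 states that quantity. It leads to the same repair.

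A second reading restricts each endpoint to eyes whose lens was selected with that formula. The available text does not say which formula selects the lens. However, a figure in section 3.2 is not shown and the Visit 1 description in section 3.4 breaks off, so no weight should rest on that silence. Even with a selection rule, the result would be separate, non-randomised subsets of eyes, not a comparison on the same eyes.

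Three further points stand. Section 5.3 does not name Visit 3; that is inferred because it is the only scheduled postoperative visit. The size of the hidden difference rests wholly on assumed SDs and biases. And these are descriptive secondary endpoints in a self-described pilot, where five identical percentages would probably be noticed. These limit the consequences but do not make the written endpoint usable.

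**Conclusion.** The concern holds. Read literally, endpoints a–e are a single proportion and cannot show any difference between formulas. That conclusion rests only on one lens and one scheduled postoperative refraction per eye, with all five endpoints taken on the same eyes. The true difference that would go unreported ranges from 0 to about 16 points, or 0 to about 10 of 60 eyes, under the assumed normal errors.

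This should be fixed, but it is a fault of definition and not of data collection.

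**What to change.** Amend section 5.3 before analysis:

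- In a–e, replace plano as the reference with each formula's own predicted refraction for the implanted power, as recorded at Visit 2.
- Define prediction error as the Visit 3 manifest spherical equivalent minus that prediction. State that the ±0.50 D limit applies to the spherical equivalent; this is an assumption here, since the documents leave it open.
- Report the proportion of eyes with absolute prediction error of 0.50 D or less for all five formulas on the same eyes.
- Report the proportion within ±0.50 D of plano once, as a surgical outcome.
- If confidence intervals are given, allow for two eyes per patient.

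In the same edit, clarify f and g. Visit 2 captures "residual astigmatism and axis for Barrett Toric Calculator and Barrett TK for toric power calculation", but section 5.3 does not say whether the scored value is each calculator's figure or the astigmatism measured at Visit 3. If it is the measured value, f and g would coincide on the same eyes in the same way.

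The cost is a rewording. The predictions and the refraction are already scheduled for collection, so no extra visits, measurements or patients are needed.

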#### 2. STUDY DESIGN AND METHODS:

- **2.1. Test article:** AcrySof® IQ PanOptix IOL (TFNT00 and TFNTx0 Alcon Laboratories).
- **2.2. Study Design:** Prospective, single center, bilateral eye study.

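### Secondary endpoints (a)-(e) reduce each formula's error to a yes/no cut at ±0.50 D, although the error in dioptres can be derived from data the plan already collects

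*Combined protocol and SAP*

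**What the plan says.** Section 5.3 lists five parallel secondary endpoints, one per formula. The first reads "Proportion of eyes within ±0.50 D of intended target (plano) when using the Barrett Universal II formula for IOL power calculation"; (b) to (e) differ only in the formula named (Hill RBF, Holladay 2, Holladay 1, SRK-T). No mean, median, absolute value or SD of the error is named as an endpoint, and no contrast between formulas is specified.

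Section 3.4 collects both parts of a continuous error. On the day of surgery the site captures "target refraction for IOL power implanted using Barrett Universal II, Hill RBF, Holladay 2, Holladay 1 and SRK-T formulas". At Month 3 the list begins "Slit lamp examination, manifest refraction, UCVA, BCVA, UCIVA (at 60 cm", so the achieved refraction is available.

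On method, Section 5.2 says only: "Statistical analysis will be performed using standard descriptive statistics". Section 5.1 states "A total of 30 subjects will be enrolled", calls the study a pilot, and says the sample size would need "an accurate estimate of the standard deviation of the outcome measure which we do not know". Section 2.2 describes a "Prospective, single center, bilateral eye study".

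**The concern.** A yes/no cut treats an eye 0.05 D from the prediction the same as one 0.49 D away, and treats 0.49 D and 0.51 D as different. Two formulas applied to the same eye differ on this measure only when one lands inside the limit and the other outside. Eyes where both are inside, or both outside, say nothing about which formula was closer, although the dioptre values do.

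Evaluating the formulas is part of the stated objective and of the title, and the study has at most 60 eyes. Five like-for-like proportions invite side-by-side reading even with no test planned. Proportions alone also do not report the error SD, which is the kind of quantity that Section 5.1 says is unknown and that a later study would need.

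**Working it through.** **Inputs from the documents.** 30 subjects (5.1), two eyes each (2.2), so at most 30 × 2 = 60 eyes. The limit is ±0.50 D (5.3). The plan's own figure of 30 matches the rule of thumb it cites, "use at least 30 subjects or greater to estimate a parameter". It has no SD, effect size, alpha or power behind it, so there is no calculation to reproduce.

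**Inputs assumed, because the documents give none.** Normal errors with mean 0; error SD and correlations as stated below; no dropout.

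**Step 1: which reference.** Read literally, the endpoint measures distance from plano. One lens is implanted per eye, so the achieved refraction is a single value per eye. Its distance from plano is the same whichever formula is named, all five proportions coincide, and no eye separates any two formulas. A comparison exists only if the error is taken as:

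error = Visit 3 manifest spherical equivalent − that formula's predicted refraction for the implanted lens.

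The steps below use this definition.

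**Step 2: one formula.** With k = 0.50/SD and p = 2Φ(k) − 1, the information on the SD kept by the indicator |error| ≤ 0.50, relative to the full normal error, is

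RE = 4k²φ(k)² / [2p(1 − p)].

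Worked case, SD 0.40 D: k = 1.25, p = 0.789, φ(k) = 0.1826. RE = 4 × 1.5625 × 0.0334 / (2 × 0.789 × 0.211) = 0.626, a loss of 37%.

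| SD (D) | p | RE | Loss |
|---|---|---|---|
| 0.25 | 0.954 | 0.537 | 46% |
| 0.30 | 0.904 | 0.636 | 36% |
| 0.35 | 0.847 | 0.651 | 35% |
| 0.40 | 0.789 | 0.626 | 37% |
| 0.45 | 0.733 | 0.585 | 41% |
| 0.50 | 0.683 | 0.541 | 46% |
| 0.60 | 0.595 | 0.458 | 54% |

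The smallest possible loss is about 35%, at SD about 0.34 D.

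**Step 3: two formulas on the same eyes.** Simulation of 30 patients and 60 eyes over 16 settings: better-formula SD 0.30 to 0.40 D, worse formula 12-20% larger, between-formula correlation 0.8 to 0.9, fellow-eye correlation 0.3 to 0.5. Eyes are averaged within patient. Relative efficiency is the squared ratio of mean to SD of the patient-level difference in the indicator, divided by the same quantity for the difference in absolute error.

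- Relative efficiency of the cut: 0.40-0.59, a loss of about 40-60%. This is like keeping 0.40 × 60 = 24 to 0.59 × 60 ≈ 35 eyes.
- Eyes in which the two formulas fall on opposite sides of the limit: on average about 5-13 of 60.
- True reversals, where the worse formula looks strictly better: about 2-16% with the cut, 0.4-13% with mean absolute error.

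Between-formula correlation drives the result. In a second set of runs (SD 0.35 to 0.40 D against 0.40 to 0.50 D, fellow-eye correlation 0.5), relative efficiency was 0.54-0.60 at correlation 0.80, 0.43-0.47 at 0.90 and 0.32-0.34 at 0.95.

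**Step 4: illustration only.** If a two-sided 5% patient-level paired test were applied in the Step 3 settings, power would be 11-36% with the cut and 20-73% with absolute error. The plan contains no such test.

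**The case against.** The strongest reply is that the plan promises description, not comparison. The objective is to evaluate the formulas, Section 5.2 is descriptive, and each endpoint is one formula's own proportion. A reader might infer that a planned ranking of formulas rests on a handful of eyes. The documents do not support that, because no ranking, test or between-formula contrast appears. This stands: the power figures can only illustrate, and for describing a single formula the loss is the smaller one in Step 2.

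A reader might also infer that the cut makes wrong ordering far more frequent throughout. That is not supported either. Counting ties as wrong inflates the contrast, since two counts can tie and two mean absolute errors practically cannot. On true reversals the gap is clear mainly at correlation 0.9 or with a 20% difference. At SD 0.30 D, 12% worse and correlation 0.8, the rates are close: 13-14% against 11-12%.

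Three further points stand. The dioptre error is derivable rather than recorded, and only for eyes that reach Visit 3. The gain appears only after the plano reference is replaced. The proportion within ±0.50 D is easy to interpret and worth keeping.

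What does not stand is that Section 5.2 already covers the matter. Descriptive statistics do not exclude a summary of the error, but nothing commits the analyst to one or says how it is defined.

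**Conclusion.** The point holds as a free improvement. Endpoints (a)-(e) summarise each formula only by a cut, while the plan's own data allow a paired error in dioptres. Under the assumed values, the cut loses about 35-46% of the information on the spread of one formula's error (SD 0.25 to 0.50 D) and about 40-60% in a side-by-side comparison over the Step 3 settings. None of these figures comes from the documents. They assume normal, centred errors and complete follow-up, and they move with the SD and the between-formula correlation. A flat statement that half the information is lost would therefore go further than the documents allow.

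The consequence is limited: these are secondary endpoints of a self-described pilot, and the sole primary endpoint concerns angle kappa.

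**What to change.** In Sections 5.2 and 5.3:

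- Define prediction error, per eye and formula, as the Visit 3 manifest spherical equivalent minus that formula's predicted refraction for the implanted lens, in place of distance from plano.
- For each formula, report the mean absolute error and the SD of the error.
- For pairs of formulas, report the within-eye difference in absolute error with a 95% interval obtained by resampling patients, so that both eyes of a patient stay together.
- Keep the ±0.50 D proportions, on the same reference, as descriptive supplements.
- State that no formal test or ranking is intended, if that is the case.

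The cost is a few sentences in the plan and a few lines of analysis code. No new data, visits or patients are needed.

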#### 2.3. Subjects:

#### 1. Inclusion Criteria:

Subjects MUST fulfill the following conditions to qualify for enrollment into the trial

- 1. Subject is undergoing bilateral lens extraction with intraocular lens implantation.
- 2. Gender: Males and Females.
- 3. Age: 40 years and older.
- 4. Willing and able to provide written informed consent for participation in the study

- 5. Willing and able to comply with scheduled visits and other study procedures.
- 6. Scheduled to undergo standard cataract surgery with topical anesthesia in both eyes within 6 to 30 days between surgeries.
- 7. Subjects who require an IOL power in the range of +6.0 D to +30.0 D only.
- 8. Subjects who require a TFNT00 or TFNT30 to TFNT60 IOL.
- 9. Potential postoperative visual acuity of 0.2 logMAR (20/32 Snellen) or better in both eyes.

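### The secondary endpoints score both eyes of each patient under every formula, but the plan provides neither a patient-clustered interval nor a paired comparison of formulas

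*Combined protocol and SAP*

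**What the plan says.** Section 2.2 describes a "Prospective, single center, bilateral eye study". The first inclusion criterion in section 2.3 is "Subject is undergoing bilateral lens extraction with intraocular lens implantation", and section 5.1 states "A total of 30 subjects will be enrolled". If everyone completes, that gives 30 × 2 = 60 eyes; the figure 60 is derived and does not appear in the plan.

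Endpoints a to e in section 5.3(2) repeat one definition for five formulas. Endpoint a is "Proportion of eyes within ±0.50 D of intended target (plano) when using the Barrett Universal II formula". Endpoints f and g are proportions of eyes with residual astigmatism of 0.50 D or less under two toric calculators. Section 3.4 (Visit 2) has the site record, for the lens power actually implanted, the refraction that each of the five formulas predicts. Toric calculations are recorded only where they apply.

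On analysis, section 5.2 says "Statistical analysis will be performed using standard descriptive statistics" and adds strata by angle kappa. It names no interval, no test, no contrast between formulas and no handling of fellow eyes. Section 1 gives evaluation of the formulas as part of the study's purpose.

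**The concern.** Two kinds of dependence are built into these endpoints. Fellow eyes share a patient, so 60 eyes are not 60 independent observations. The five formulas are scored on the same eyes, so their proportions are repeated measures and not five samples. The plan provides for neither.

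The sample-size rule counts patients while the endpoints count eyes, and nothing links the two units. Section 5.2 hands the analysis to an outside consultant, and section 11 plans publication. An analyst given eye proportions and no further instruction could readily attach binomial intervals with n = 60 and compare formulas as if unpaired. The first makes each formula's result look more precise than it is. The second usually hides part of the trial's ability to tell formulas apart.

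**Working it through.** **The plan's own figure.** The only one is N = 30. It equals the quoted rule, "use at least 30 subjects or greater to estimate a parameter". No alpha, power or effect is given, and section 5.1 says the calculation would need "an accurate estimate of the standard deviation of the outcome measure which we do not know". No precision figure is stated for the secondary endpoints, so there is none to reproduce.

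**Inputs.** From the plan: 30 patients, two eyes each, the same eyes under all formulas. Assumed: normal prediction errors with mean 0 and SD 0.40 D; correlation between fellow-eye errors of 0.3, 0.5 or 0.7; correlation between two formulas on one eye of 0.70, 0.85 or 0.95; correlation across both eye and formula equal to the product of the two. Each setting was simulated 20,000 times and checked against the formulas below.

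**Step 1, the proportion.** p = P(|Z| < 0.50/0.40 = 1.25) = 0.789.

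**Step 2, one formula.** Naive SE = √(0.789 × 0.211 / 60) = 5.27 points. With pairs of eyes it is multiplied by √(1 + ICC), where ICC is the correlation between the two eyes' yes/no results.

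| Fellow-eye r (errors) | ICC (yes/no) | SE, points | Coverage of naive 95% Wald interval |
|---|---|---|---|
| 0 | 0 | 5.27 | 93.7% (exact) |
| 0.3 | 0.057 | 5.27 × √1.057 = 5.4 | about 93% |
| 0.5 | 0.163 | 5.27 × √1.163 = 5.7 | about 91.5% |
| 0.7 | 0.334 | 5.27 × √1.334 = 6.1 | about 89% |

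The proper benchmark is 93.7%, because the Wald interval already falls about 1.3 points short of 95% with 60 independent eyes. Clustering itself costs about 1, 2 and 4 points.

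If the ICC is assumed directly, with p = 0.80, the naive half-width is 1.96 × √(0.16/60) = 10.1 points. It becomes 11.5 at ICC 0.3, 12.4 at 0.5, and 14.3 at the ceiling of 1.0, where the factor is √2.

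**Step 3, a difference between two formulas.** Treated as separate samples, SE = √(2 × 0.789 × 0.211 / 60) = 7.45, or 7.5 points. Pairing multiplies this by √(1 − φ), where φ is the yes/no agreement correlation between formulas. Fellow-eye correlation then adds some back.

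| Between-formula r | φ | Paired SE, eyes independent | Paired SE, fellow-eye r 0.3 to 0.7 |
|---|---|---|---|
| 0.70 | 0.33 | 6.1 | 6.2 to 6.9 |
| 0.85 | 0.53 | 5.1 | 5.2 to 5.7 |
| 0.95 | 0.72 | 3.9 | 4.0 to 4.2 |

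**Step 4, what the endpoint measures.** One lens goes into each eye and gives one achieved refraction. Its distance from plano is therefore the same number whichever formula is named. Read literally, endpoints a to e would be five identical proportions and every paired difference would be zero. The comparison has content only if each formula is scored by achieved refraction minus the refraction it predicted for the implanted power, which Visit 2 records.

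**Step 5, toric endpoints.** A patient may contribute 0, 1 or 2 toric eyes, so 60 is not the denominator for f and g. The number of toric eyes is not given. If it were 20 with p = 0.80, the half-width would be 1.96 × √(0.16/20) = 17.5 points before any clustering.

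**The case against.** The strongest reply is that the plan contains no wrong precision figure. It is descriptive, it says "we consider this study a pilot trial", and it states no interval, test or formula contrast. A reader might infer that precision will be misjudged in both directions. The documents do not support that: an error would arise only if a later analyst attached the ordinary methods. A reader might also infer that the proportions themselves are biased. They are not, since with two eyes from every patient the eye-level proportion is an unbiased estimate. A table of paired proportions is also legitimate description. All of this stands.

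The two directions also concern different quantities, and the second is not guaranteed. With proportions of 0.80 and 0.70, φ = 0.3 and an ICC of 0.5 in the paired difference, the correct half-width is 15.8 points against 15.4 unpaired, so the two effects cancel. That combination did not occur in the range simulated: at between-formula r 0.70 (φ about 0.33) the paired SE was still 8% to 17% below the unpaired one. But every correlation here is assumed, so the possibility remains.

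Finally, the single-proportion effect is small at low fellow-eye correlation, and these are secondary endpoints. That limits the weight of the point. It does not supply the missing method: a study sized to estimate a parameter needs to say how precisely it has done so.

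**Conclusion.** The point holds as a gap in the analysis plan, not as an error in a stated result. The unit, the two eyes per patient and the shared eyes across formulas all follow from the text, and section 5.2 provides for none of the resulting dependence. The formula question in the objective is thus left without a valid interval or a defined comparison.

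The effect on single-formula precision is modest. The effect on comparing formulas is larger: an unpaired interval would be about 1.1 times (7.45/6.9) to 1.9 times (7.45/4.0) as wide as needed over the range examined. These sizes rest on an assumed error SD, proportion within range and correlations, none of which the plan gives. The direction for a single proportion needs only a positive correlation between fellow eyes. The direction for a difference needs reasonable agreement between formulas on the same eye.

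**What to change.** In sections 5.2 and 5.3(2):

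- Define endpoints a to e on prediction error, that is, achieved refraction minus the refraction each formula predicted for the implanted power, and reconcile this with the present wording about plano.
- Keep the eye-level proportions as point estimates and give each a 95% confidence interval clustered by patient, from a patient-level bootstrap or a GEE with patient as the cluster.
- Compare formulas within eye, as paired differences in the proportion within ±0.50 D and in absolute prediction error, using the same patient-level bootstrap.
- Report the number of patients and of eyes for every endpoint, with f and g limited to toric eyes.

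The cost is a few sentences of analysis text and a little programming. Single-formula intervals become slightly wider. No new patients or measurements are needed.
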